6.2.4. Phase 1b Dose Period 3 (Day 35 and Day 37)

Dose Period 3 consists of Day 35 and Day 37. The visit window for Dose Period 3 is +/- 3 days of the scheduled visit.

Day 35 procedures will be performed in the following order:

- Physical examination;
- Weight, and vital signs (blood pressure, temperature and heart rate);
- Urine pregnancy test (female);
- Blood sample for hematology and serum chemistry tests;
- Administer IMU-131 vaccination;
- Record body temperature 30 (+/-10) minutes after vaccination;
- Record concomitant treatments;
- Record adverse events;
- Initiate chemotherapy cycle 2.

Day 37 procedures will be performed in the following order:

- Vaccination site evaluation for local effects;
- Record concomitant treatments;
- Record adverse events.

6.2.5. Phase 1b End of Treatment Visit (Day 56)

The end of treatment visit occurs on Day 56. The allowable visit window for this visit is +/- 3 days.

End of treatment/Day 56 procedures will be performed in the following order:

- Physical examination;

Investigational Product: IMU-131
Protocol Identifier: IMU.ACS.001
Protocol Version: Protocol Global Amendment #5, 27 September 2023

- Weight, and vital signs (blood pressure, temperature and heart rate);
- Blood sample for hematology and serum chemistry tests;
- Blood sample for immunology tests;
- Cardiac assessment by echocardiography or MUGA scan and 12-lead ECG;
- Radiographic assessment;
- Record concomitant treatments;
- Record adverse events;
- Initiate chemotherapy cycle 3.

6.2.6. Phase 1b chemotherapy only visit (Day 77)

Day 77 is for continuation of chemotherapy, as determined by the study investigator. A visit window of +/- 7 days is allowable.

Day 77 procedures will be performed in the following order:

- Physical examination;
- Weight, and vital signs (blood pressure, temperature and heart rate);
- Blood sample for hematology and serum chemistry tests;
- Record concomitant treatments;
- Record adverse events;
- Initiate chemotherapy cycle 4.

6.2.7. Phase 1b Follow-up Post-Withdrawal Visit (30 – 40 days after last vaccination)

A visit window of - 2 days to +16 days is allowable.

When the patient is withdrawn during either Phase 1b or Long Term Maintenance this visit occurs 30 – 40 days after the last vaccination. The subject summary page of the CRF should be completed after this visit has occurred.

Follow-up post withdrawal procedures will be performed in the following order:

- Physical examination;
- Weight, and vital signs (blood pressure, temperature and heart rate);
- Urine pregnancy test (female);
- Record concomitant treatments (medications and procedures);
- Record adverse events.

6.2.8. Phase 1b Unscheduled Visit

Unscheduled visits may be conducted at any time during Phase 1b or Long Term Maintenance by the investigator if clinically indicated for the care of the patient.

Investigational Product: IMU-131
Protocol Identifier: IMU.ACS.001
Protocol Version: Protocol Global Amendment #5, 27 September 2023

An unscheduled visit may include any of the protocol required assessments listed in [Section 7](#): Phase 1b Assessments. The exact assessments conducted at the unscheduled visit will be specified by the investigator and recorded in the CRF. Additional tests and procedures may be performed at the unscheduled visit for the clinical care of the patient after discussion with, and agreement of, the medical monitor.

6.3. Phase 1b Long Term Maintenance of Phase 1b patients (Day 98 onwards)

Patients completing the End of Treatment/Day 56 assessment in Phase 1b will move into long term maintenance starting at Day 98. Long term maintenance will continue until the patient is no longer participating in the study, or IMU-131 has been shown to be of no clinical benefit, its development is discontinued or the Sponsor decides to terminate the study prematurely. Patients will discontinue participation in long term maintenance when there is documented evidence of disease progression according to RECIST 1.1 response criteria or if unacceptable toxicity occurs. The last long term maintenance visit prior to discontinuation will be recorded as the end of treatment visit for long term maintenance. The Phase 1b follow-up post withdrawal visit ([Section 6.2.7](#)) will be conducted 30 – 40 days after the last vaccination during long term maintenance.

In addition to booster vaccinations most likely every 12 weeks each Long Term Maintenance visit will include a urine pregnancy test, collection of blood samples for hematology, serum chemistry and titer kinetic evaluation, a physical examination including vital signs (BP, pulse and temperature), a radiographic assessment and collection of adverse event and concomitant medication data. For details of the procedures and timing of visits during Long Term Maintenance see [Table 2](#): Schedule of Activities Long Term Maintenance.

Humoral and cellular immunogenicity data will include P467-specific antibodies (IgG) and Her-2- specific antibodies (IgG) in serum samples and vaccine-specific cytokine levels as well as analysis of regulatory and effector T and B cells will continue to be collected when booster vaccinations are given (i.e. every 12 weeks) during long-term maintenance. The dose of booster vaccinations will be determined and vaccination interval confirmed by the titer kinetics evaluated in Phase1b, details of which will be provided for ethical and regulatory review as an amendment to this protocol.

6.4. Phase 2 and Phase 2 Extension Study Period

6.4.1. Phase 2 and Phase 2 Extension Vaccination procedure

All vaccinations must be administered in an appropriate medical facility equipped for immediate intervention in the event of an allergic reaction.

Preparation of IMU-131 is to be conducted precisely according to instruction in [Section 5.2.2](#) Preparation and Dispensing. Prior to vaccination patient's vital signs (blood pressure, pulse, temperature) will be measured. IMU-131 vaccine should be administered intramuscularly (IM) into the deltoid region of the upper arm with a 25-38mm (1-1.5 inches), 21-23G needle needle. The vaccination site should be disinfected with a skin disinfectant (e.g., 70% alcohol) prior to vaccination of study drug IM. The vaccine must not be injected into blood vessels and the Medical Professional administering the

Investigational Product: IMU-131
Protocol Identifier: IMU.ACS.001
Protocol Version: Protocol Global Amendment #5, 27 September 2023

injection must confirm IM placement via a “negative” blood return on a “pull back” check before injecting IMU-131.

Patients will be observed for at least 30 minutes after vaccination, with appropriate medical treatment readily available in case of a rare anaphylactic reaction following the administration. Any reactions that occur during this time must be recorded by the investigator in the CRF. Thirty minutes (+/- 10 min) after vaccination, the patient’s temperature will be recorded.

Patients will be instructed to contact the investigator immediately should they manifest any signs or symptoms they perceive as serious.

6.4.2. Phase 2 and Phase 2 Extension Baseline/Day 0

There is no allowable visit window for Baseline/Day 0. Day 0/Baseline procedures should be performed in the following order:

- Blood sample for hematology and serum chemistry (Screening safety lab samples taken within 72 hours of first study treatment do not need to be repeated on Day 0);
- Blood sample for humoral and cellular immunology;
- Blood sample for exploratory endpoints;
- Weight, and vital signs (blood pressure, temperature and heart rate);
- Urine pregnancy test (female);
- Physical examination;
- ECOG performance score;
- Radiographic assessment (Allowed during screening period - up to 14 days prior to Day 0)
- Administer IMU-131 vaccination and record body temperature 30 (+/-10) minutes after vaccination (only for patients in IMU-131 plus chemotherapy group);
- Record concomitant treatments;
- Record adverse events;
- Initiate chemotherapy cycle 1.

6.4.3. Phase 2 and Phase 2 Extension Week2/Day 14 (only for patients in IMU-131 plus chemotherapy cohorts)

The visit window for Day 14 is +/- 3 days of the scheduled visit. Day 14 procedures should be performed in the following order:

- Weight, and vital signs (blood pressure, temperature and heart rate);
- Urine pregnancy test (female);
- Administer IMU-131 vaccination;
- Record body temperature 30 (+/-10) minutes after vaccination;

Investigational Product: IMU-131
Protocol Identifier: IMU.ACS.001
Protocol Version: Protocol Global Amendment #5, 27 September 2023

- Record concomitant treatments;
- Record adverse events.

6.4.4. Phase 2 and Phase 2 Extension Week 3/Day 21

The visit window for Day 21 is +/- 3 days of the scheduled visit. Day 21 procedures should be performed in the following order:

- Blood sample for hematology and serum chemistry;
- Blood sample for humoral immunology;
- Weight, and vital signs (blood pressure, temperature and heart rate);
- Urine pregnancy test (female);
- Physical examination;
- Record concomitant treatments;
- Record adverse events;
- Initiate chemotherapy cycle 2.

6.4.5. Phase 2 and Phase 2 Extension Week 5/Day 35 (only for patients in IMU-131 plus chemotherapy cohorts)

The visit window for Day 35 is +/- 3 days of the scheduled visit. Day 35 procedures should be performed in the following order:

- Weight, and vital signs (blood pressure, temperature and heart rate);
- Urine pregnancy test (female);
- Administer IMU-131 vaccination;
- Record body temperature 30 (+/-10) minutes after vaccination;
- Record concomitant treatments;
- Record adverse events.

6.4.6. Phase 2 and Phase 2 Extension Week 6/Day 42

The visit window for Day 42 is +/- 3 days of the scheduled visit. Day 42 procedures should be performed in the following order:

- Blood sample for hematology and serum chemistry;
- Blood sample for humoral immunology;
- Weight, and vital signs (blood pressure, temperature and heart rate);
- Urine pregnancy test (female);
- Physical examination;
- Radiographic assessment;
- Record concomitant treatments;

Investigational Product: IMU-131
Protocol Identifier: IMU.ACS.001
Protocol Version: Protocol Global Amendment #5, 27 September 2023

- Record adverse events;
- Initiate chemotherapy cycle 3.

6.4.7. Phase 2 and Phase 2 Extension Week 9/Day 63

The visit window for Day 63 is +/- 7 days of the scheduled visit. Day 63 procedures should be performed in the following order:

- Blood sample for hematology and serum chemistry;
- Blood sample for humoral immunology;
- Weight, and vital signs (blood pressure, temperature and heart rate);
- Urine pregnancy test (female);
- Physical examination;
- Record concomitant treatments;
- Record adverse events;
- Initiate chemotherapy cycle 4.

6.4.8. Phase 2 and Phase 2 Extension Week 11/Day 77 (only for patients in IMU-131 plus chemotherapy cohorts)

The visit window for Day 77 is +/- 7 days of the scheduled visit. Day 77 procedures should be performed in the following order:

- Weight, and vital signs (blood pressure, temperature and heart rate);
- Urine pregnancy test (female);
- Administer IMU-131 vaccination;
- Record body temperature 30 (+/-10) minutes after vaccination;
- Record concomitant treatments;
- Record adverse events.

6.4.9. Phase 2 and Phase 2 Extension Week 12/Day 84 (Repeat every 12 weeks/84 days)

The visit window for Day 84 is +/- 7 days of the scheduled visit. Day 84 procedures should be performed in the following order:

- Weight, and vital signs (blood pressure, temperature and heart rate);
- Blood sample for hematology and serum chemistry;
- Blood sample for humoral and cellular immunology;
- Blood sample for exploratory endpoints;
- Urine pregnancy test (female);
- Physical examination;
- ECOG performance score;

Investigational Product: IMU-131
Protocol Identifier: IMU.ACS.001
Protocol Version: Protocol Global Amendment #5, 27 September 2023

- Cardiac assessment by echocardiography or MUGA scan and 12-lead ECG;
- Radiographic assessment;
- Optional tumor biopsy sample (at Day 84);
- Record concomitant treatments;
- Record adverse events;
- Initiate chemotherapy cycle 5.

6.4.10. Phase 2 and Phase 2 Extension Week 15/Day 105

The visit window for Day 105 is +/- 7 days of the scheduled visit. Day 105 procedures should be performed in the following order:

- Blood sample for hematology and serum chemistry;
- Weight, and vital signs (blood pressure, temperature and heart rate);
- Urine pregnancy test (female);
- Physical examination;
- Record concomitant treatments;
- Record adverse events;
- Initiate chemotherapy cycle 6.

6.4.11. Phase 2 and Phase 2 Extension Week 18/Day 126 (Repeat every 12 weeks/84 days)

The visit window for Day 126 is +/- 7 days of the scheduled visit. Day 126 procedures should be performed in the following order:

- Blood sample for hematology and serum chemistry;
- Blood sample for humoral immunology;
- Weight, and vital signs (blood pressure, temperature and heart rate);
- Urine pregnancy test (female);
- Physical examination;
- Radiographic assessment;
- Record concomitant treatments;
- Record adverse events;

6.4.12. Phase 2 and Phase 2 Extension Week 20/Day 140 (Repeat every 9 week/63 days - only for patients in IMU-131 plus chemotherapy cohorts)

The visit window for Day 140 is +/- 7 days of the scheduled visit. Day 140 procedures should be performed in the following order:

- Weight, and vital signs (blood pressure, temperature and heart rate);

Investigational Product: IMU-131
Protocol Identifier: IMU.ACS.001
Protocol Version: Protocol Global Amendment #5, 27 September 2023

- Urine pregnancy test (female);
- Administer IMU-131 vaccination;
- Record body temperature 30 (+/-10) minutes after vaccination;
- Record concomitant treatments;
- Record adverse events.

6.4.13. Phase 2 and Phase 2 Extension End of Treatment (EoT) Visit

When progressive disease or withdrawal from study has been confirmed, the EoT visit will be conducted at least 28 Days (+/- 7) after last dose of study medication. An optional post-progression tumor biopsy sample will be requested from patients and may be provided at any time post progression. EoT visit procedures should be performed in the following order:

- Weight, and vital signs (blood pressure, temperature and heart rate);
- Blood sample for hematology and serum chemistry;
- Blood sample for humoral and cellular immunology;
- Blood sample for exploratory endpoints;
- Urine pregnancy test (female);
- Physical examination;
- ECOG performance score;
- Cardiac assessment by echocardiography or MUGA scan and 12-lead ECG;
- Record concomitant treatments;
- Record adverse events (AEs to be checked at least 28 days after last study treatment per [Section 9.2: Reporting Period](#)).

6.4.14. Phase 2 Post-Treatment Follow-up Visit (Every 42 days after EoT visit)

This visit may be conducted via phone, email, review of medical records or via publicly available information. A visit window of +/- 7 days is allowable.

- Radiographic assessment (only for patients who withdrew from study before progressive disease was confirmed);
- Record survival follow-up assessment;
- Record post-study anti-cancer treatment.

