- B A 1 x 10 mL whole blood sample to assess vaccine-specific cytokine levels and in-vitro inhibition of tumor cell growth will be obtained from each patient at Days 0, 84 then every 84 days and at EoT visit.

Investigational Product: IMU-131
Protocol Identifier: IMU.ACS.001
Protocol Version: Protocol Global Amendment #5, 27 September 2023

- C 1 x 10 mL (i.e. 1 tube) whole blood sample for humoral immunity at Baseline, Days 21, 42, 63, 84, 126 then every 42 days and EoT visit and 40 mL blood sample at Screening (Phase 2 Extension only), Baseline, Days 84 then every 84 days and EoT visit for cellular immunity. To be taken prior to vaccination at Baseline visit.
- D Chemotherapy will be administered as a concomitant therapy to all patients as a 21-day regimen consisting of: cisplatin by intravenous administration at 80 mg/m² on the first day of each cycle and either 5-FU, 4000 mg/m² CIV (administered as 1000 mg/m²/day as continuous infusion for 96 hours on days 1 to 4 of each cycle) or capecitabine for 14 days at 2000 mg/m²/day, orally (administered as 1000 mg/m² twice daily morning and evening for a total of 2000 mg/m²/day on days 1 to 14 of each cycle), or capecitabine for 14 days at 2000 mg/m²/day, orally (administered as 1000 mg/m² twice daily morning and evening for a total of 2000 mg/m²/day on days 1 to 14 of each cycle) and oxaliplatin, by intravenous administration at 130 mg/m² on Day 1 of each cycle. Body weight to be measured and body surface area to be calculated based on weight and baseline height at the start of each 21-day chemotherapy cycle. Chemotherapy continues until ceased by the investigator as clinically indicated for the care of the patient. To document compliance while away from the clinic, patients will record capecitabine treatment in a patient diary.
- E Radiographic assessment to occur within 14 days prior to Baseline Visit, then at Days 42, 84, 126 every 42 days thereafter. Radiographic assessment continues until disease progression according to RECIST 1.1 response criteria, withdrawal or end of trial.
- F Chemotherapy continues for up to 6 cycles until disease progression or until ceased by the investigator as clinically indicated for the care of the patient, whichever occurs first.
- G Radiographic assessment according to RECIST 1.1 response criteria at post-treatment follow-up visit only for patients who have ended study treatment prior to disease progression.

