8.1. Assessments via Telemedicine

Telemedicine uses advanced telecommunication technologies to exchange health information and provide health care services across geographic, social, and other barriers. Where circumstances allow, and where additional flexibility is required due to restricted patient access to the study clinic or personnel, telemedicine technology may be used to collect study data to supplement study assessments. For example, visits may be conducted over several days within each visit window, with suitable assessments being completed using telemedicine technology with the remaining assessments being completed during a physical clinic visit. Examples of study assessments which may be completed using telemedicine technology include documenting concomitant treatments and adverse events, ECOG performance grade, and survival follow-up.

Investigational Product: IMU-131
Protocol Identifier: IMU.ACS.001
Protocol Version: Protocol Global Amendment #5, 27 September 2023

8.2. Phase 2 and Phase 2 Extension Physical Examination (Screening, Baseline, Days 21, 42, 63, 84, 105, 126 then every 42 days and EoT visit)

The physical examination will include an evaluation of body systems (e.g. cardiovascular, gastrointestinal, neurological, head and neck, respiratory, dermatology). After the Baseline physical examination, a symptom-directed physical examination is allowed at subsequent visits at the investigator's discretion.

8.3. Phase 2 and Phase 2 Extension Height, Weight, Vital Signs, Concomitant Medications, Concomitant Procedures and Adverse Events (at each study visit, excluding post-treatment follow-up visits)

Body height (at screening visit only), weight, and vital signs (blood pressure, pulse and temperature) will be measured and concomitant medications, concomitant procedures and adverse events will be documented.

8.4. Phase 2 and Phase 2 Extension Radiographic Assessment (Baseline, Days 42, 84, 126 then every 42 days)

For all patients a radiographic assessment will be performed at Baseline (assessment allowed up to 14 days before Baseline Visit), Days 42, 84, 126 then every 42 days until disease progression. Assessment of the tumor will include evaluation according to RECIST 1.1.

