**Table 8-1 Censoring Conventions for PFS**

Situation	Date of Progression or Censoring	Outcome
Disease progression, and time interval between progression date and previous tumor assessment date with progression-free response is less than or equal to 98 days	Earliest of: 

• Date of first tumor assessment showing new lesion

• Date of first tumor assessment with overall response of PD

	Event
Disease progression, and time interval between the progression date and the previous tumor assessment date with progression-free response is greater than 98 days.	Latest of: 

• the last progression-free assessment date

• randomization date

	Censored
Death without any post-baseline radiological assessment, and time interval between death	Death date	Event

date and randomization date is less than or equal to 98 days		
Death without any post-baseline radiological assessment, and time interval between death date and randomization date is greater than 98 days	Randomization date	Censored
Death before documented progression, and time interval between death date and previous tumor assessment date with progression-free response is less than or equal to 98 days	Death date	Event
Death before documented progression, and time interval between death date and previous tumor assessment date with progression-free response is greater than 98 days	The last progression-free assessment date	Censored
No death or disease progression, no treatment discontinuation due to symptomatic deterioration, and no subsequent anti-cancer therapy (i.e., systemic anti-cancer therapy, anti-cancer surgery, curative radiotherapy).	Latest of 
 
• the last progression-free assessment date
 
• randomization date
 
	Censored
Subsequent anti-cancer treatment (i.e., systemic anti-cancer therapy, anti-cancer surgery, radiotherapy) started prior to progression	Latest of 
 
• the last progression-free assessment date prior to start of anti-cancer treatment
 
• randomization date
 
	Censored
Treatment discontinuation due to symptomatic deterioration prior to disease progression	Latest of 
 
• the last progression-free assessment date before treatment discontinuation date
 
• randomization date
 
	Censored

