B A 1 x 10 mL whole blood sample to assess vaccine-specific cytokine levels and in-vitro inhibition of tumor cell growth will be obtained from each patient at Days 0, 84 then every 84 days and at EoT visit.

C 1 x 10 mL (i.e. 1 tube) whole blood sample for humoral immunity at Baseline, Days 21, 42, 63, 84, 126 then every 42 days and EoT visit and 5 x 8 mL blood samples at Baseline, Days 84 then every 84 days and EoT visit for cellular immunity. To be taken prior to vaccination at Baseline visit.

D Chemotherapy will be administered as a concomitant therapy to all patients as a 21-day regimen consisting of: cisplatin by intravenous administration at 80 mg/m^2 on the first day of each cycle and either 5-FU, 4000 mg/m^2 CIV (administered as 1000 mg/m^2/day as continuous infusion for 96 hours on days 1 to 4 of each cycle) or capecitabine for 14 days at 2000 mg/m^2/day, orally (administered as 1000 mg/m^2 twice daily morning and evening for a total of 2000 mg/m^2/day on days 1 to 14 of each cycle), or capecitabine for 14 days at 2000 mg/m^2/day, orally (administered as 1000 mg/m^2 twice daily morning and evening for a total of 2000 mg/m^2/day on days 1 to 14 of each cycle) and oxaliplatin, by intravenous administration at 130 mg/m^2 on Day 1 of each cycle. Body weight to be measured and body surface area to be calculated based on weight and baseline height at the start of each 21-day chemotherapy cycle. Chemotherapy continues until ceased by the investigator as clinically indicated for the care of the patient. To document compliance while away from the clinic, patients will record capecitabine treatment in a patient diary.

E Radiographic assessment to occur within 14 days prior to Baseline Visit, then at Days 42, 84, 126 every 42 days thereafter. Radiographic assessment continues until disease progression according to RECIST 1.1 response criteria irrespective of whether patient has withdrawn from the study.

F Chemotherapy continues for up to 6 cycles until disease progression or until ceased by the investigator as clinically indicated for the care of the patient, whichever occurs first.

G Radiographic assessment according to RECIST 1.1 response criteria at post-treatment follow-up visit only for patients withdrawn from the study prior to disease progression.

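### Protocol and SAP conflict on when a Phase 2 patient who stops without progression is next scanned; if scans are timed from the EoT visit, the gap can reach 104–105 days and pass the SAP's 98-day censoring limit

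*Protocol*

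**What the plan says.** **On study.** Protocol section 8.4 sets scans for all patients at baseline and at "Days 42, 84, 126 then every 42 days until disease progression".

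**At the end of treatment.** Section 6.4.13 triggers the EoT visit with the words "When progressive disease or withdrawal from study has been confirmed" and says that "the EoT visit will be conducted at least 28 Days (+/- 7) after last dose of study medication". Its procedure list has no radiographic assessment, and the EoT cell of that row in Table 3 is blank.

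**After EoT.** Section 6.4.14 is headed "Phase 2 Post-Treatment Follow-up Visit (Every 42 days after EoT visit" and adds "A visit window of +/- 7 days is allowable". It provides a scan only for patients who left the study before progression was confirmed. Table 3 footnote G gives the same slot to patients who ended study treatment before progression, which is a different trigger. The body of section 8.12 asks for imaging every six weeks until progression and gives no anchor; only its heading mentions EoT.

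**When on-study scanning ends.** Protocol Table 3 footnote E: "Radiographic assessment continues until disease progression according to RECIST 1.1 response criteria, withdrawal or end of trial". SAP Appendix 1 footnote E: "Radiographic assessment continues until disease progression according to RECIST 1.1 response criteria irrespective of whether patient has withdrawn from the study".

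**Censoring.** SAP Table 8-1 has a row for "Disease progression, and time interval between the progression date and the previous tumor assessment date with progression-free response is greater than 98 days". The PFS time is then censored at the last progression-free assessment, or at randomization if that is later. Table 8-2 applies the same rule to TTP.

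**The concern.** Under protocol footnotes E and G with section 6.4.14, the scan clock for a patient who stops without progression restarts from EoT. That visit comes about four weeks after the last dose, carries no scan, and is followed by a further six weeks before the next one. The 98-day limit can then be exceeded by a patient who has kept every visit. A real progression would be removed from the event count and replaced by a censoring time well before it.

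The start of the clock also depends on the last dose. Once chemotherapy has ended, only the vaccine arm still receives doses, so patients who withdraw on the same day can be scanned on different days according to arm. In an open-label trial whose PFS analysis is triggered by 24 events, detection times for PFS and TTP should not depend on arm.

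**Working it through.** **Inputs.**
- Scan days: 0, 42, 84, 126, 168, 210, 252, 294 and so on (section 8.4).
- Vaccination days: 0, 14, 35, 77, 140, then every 63 days, so 203, 266, 329 and so on (section 3).
- Chemotherapy in both arms: cycles start on Days 0, 21, 42, 63, 84 and 105, with a maximum of six (section 5.2.3). Capecitabine runs 14 days per cycle, so its last days are 13, 34, 55, 76, 97 and 118. 5-FU runs four days per cycle.
- EoT: last dose + 28. First follow-up visit: EoT + 42.
- Assumption: chemotherapy counts as study medication for the 28-day wait, as it must in the control arm.

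**The 98-day limit.** The SAP gives no derivation. It equals 2 × 42 + 2 × 7 = 98, which is one missed scan on the 42-day calendar plus two 7-day windows. That origin is an inference.

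**Gap if scans are timed from EoT.** With last progression-free scan on Day S and last dose on Day D, the gap is (D − S) + 28 + 42 = (D − S) + 70. It exceeds 98 when D − S is more than 28.

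| Last dose | D | S | Gap (days) |
|---|---|---|---|
| Vaccine | 35, 77, 203, 329 | 0, 42, 168, 294 | 35 + 70 = 105 |
| Vaccine | 140, 266 | 126, 252 | 14 + 70 = 84 |
| Capecitabine, cycles 2, 4, 6 | 34, 76, 118 | 0, 42, 84 | 34 + 70 = 104 |
| 5-FU, fourth day of cycles 2, 4, 6 | 24, 66, 108 | 0, 42, 84 | 24 + 70 = 94 |

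Example: with last scan on Day 168 and last vaccination on Day 203, EoT is Day 231 and the next scan Day 273. The gap is 273 − 168 = 105, so a progression seen on Day 273 is censored at Day 168. If the scan due on Day 210 is done, the gap is 273 − 210 = 63 and the progression counts.

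With EoT and follow-up both 7 days late, 105 becomes 119. With both 7 days early it becomes 91, which is an event.

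**Withdrawal days that produce a gap above 98.** For withdrawal on day w, take EoT = max(w, D + 28).

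| Withdrawal period | Vaccine arm | Control arm |
|---|---|---|
| Days 0–125, capecitabine | 39 of 126 | 39 of 126 |
| Days 0–125, 5-FU | 14 of 126 | 0 of 126 |
| Days 126–251, either regimen | 7 of 126 (Days 203–209) | 0 of 126 |

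The 39 days are 29–41, 71–83 and 113–125. The 14 days are 35–41 and 77–83. After Day 126 the pattern repeats every 126 days (Days 329–335 next), so the exposure is 7/126 = 5.6%.

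**Control arm from Day 126.** A patient leaving up to 42 days after a scan has a nominal gap of at most 42 + 42 = 84 days. Two windows of +7 give 98, still an event. A last scan 7 days early gives 105.

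**Difference in detection time.** For withdrawal on the same day after chemotherapy has ended:

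| Withdrawal | Next scan, vaccine | Next scan, control | Difference |
|---|---|---|---|
| Day 141 | Day 210 | Day 183 (188 after six full capecitabine cycles) | 27 (22) days |
| Day 204 | Day 273 | Day 246 | 27 days |
| Day 211 | Day 273 | Day 253 | 20 days |

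**If scans stay on the Day 0 calendar.** The gap is 42 days, at most 42 + 14 = 56 with windows, and at most 84 + 14 = 98 with one missed scan, which the SAP still counts as an event.

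**Size.** Assume that 10–20% of 36 patients (4–7) stop without progression.
- If all stop before Day 126 on capecitabine and all progress at that first scan, 4–7 × 39/126 = 1.2–2.2 events are lost across both arms.
- If all stop after Day 126, with half in the vaccine arm, 2–3.5 × 7/126 = 0.1–0.2 events are lost.
- Each lost event is 1/24 = 4.2% of the planned total.

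**The case against.** The strongest objection is that the restart is not established. Section 8.4 scans every patient until progression, section 8.12 asks for six-weekly imaging after discontinuation, and SAP footnote E disregards withdrawal. On that text the gap stays at 42 days and no progression is lost. This stands: the long gap is a consequence of one reading. It does not remove the problem, because footnote E and section 6.4.14 are also current protocol text and a site can follow them. The SAP states that it was written for Amendment 3 and the protocol is now Amendment 5, so the footnotes may simply have drifted apart. That would not settle the conflict with section 8.4 inside the protocol itself.

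A reader might infer a systematic bias towards the vaccine, with 4–8% of PFS events lost. The documents do not support that:
- Late exposure covers 5.6% of withdrawal days, and only if the scan due within the following week is not done.
- The larger early exposure, through capecitabine, is the same in both arms.
- The control arm is not fully protected: section 5.2.3 permits chemotherapy delays, which can carry doses past Day 126, and stacked windows can bring a control gap to about 105 days.
- Progression must appear at the first follow-up scan. Later follow-up scans are 42 days apart and count as events.
- Stops for symptomatic deterioration, and new anti-cancer therapy before progression, are censored by other rows of Table 8-1 in any case.
- Section 6.4.15 allows a scan at an unscheduled visit, and SAP section 8.2.1 accepts unscheduled assessments.

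**Conclusion.** The documents contradict each other on scan timing after a stop without progression, and the passages must be reconciled. If scans are timed from EoT, gaps of 104–105 days are reachable on scheduled days, and the SAP turns a progression found at that scan into an earlier censored time. On nominal days the exposure differs by arm in two places: before Day 126 among 5-FU patients, and after Day 126 for withdrawal in the week following alternate vaccinations. More generally, the next scan can come about 20–27 days later in a vaccine patient than in a control who leaves on the same day after chemotherapy has ended.

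The likely cost is none or one of 24 PFS events. The upper figure of about two rests on an assumed stopping rate and on every affected patient progressing at that one scan. OS, the primary endpoint, is unaffected. This is a cheap improvement to the secondary endpoints and no threat to the trial's main conclusion.

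**What to change.** Reconcile Protocol Table 3 footnotes E and G, sections 6.4.14, 8.4 and 8.12, and SAP Appendix 1 footnote E. For Phase 2, state that scans stay on the 42-day calendar counted from Day 0 until progression, death, withdrawal of consent or end of trial, regardless of treatment discontinuation or the timing of EoT. Use the same trigger wording throughout, and limit withdrawal in footnote E to withdrawal of consent. Anchor only the survival and anti-cancer therapy contacts on EoT.

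If Phase 2 scanning is already complete, list by arm the progressions found more than 98 days after the last progression-free scan, and add a PFS and TTP sensitivity analysis that counts them as events on the date found.

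The cost is wording in both documents and at most about one additional routine scan per affected patient. The retrospective version needs one listing and one additional analysis. Nothing here alters when treatment stops.
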